2.3. Primary Endpoint

The primary endpoint is the reduction from baseline in Modified Mayo Score at Week 8.

2.4. Secondary Endpoints

The secondary endpoints of this study are:

- Number and rate of patients in clinical remission at Week 8, per each intervention/treatment group. Clinical remission, based on the Mayo Scoring system, is defined as stool frequency subscore = 0 or 1 and rectal bleeding subscore = 0 and endoscopy subscore = 0 or 1 (modified to exclude friability).

- Combined number and rate of patients in clinical remission at Week 8 and at Week 16, per each intervention/treatment group.
- Number and rate of patients with clinical response at Week 8 and Week 16 per intervention/treatment group. Clinical Response is defined as a reduction in Mayo Score of at least 2 points and greater than or equal to 30 percent from baseline with an accompanying decrease in rectal bleeding sub-score of greater than or equal to 1 point or absolute rectal bleeding sub-score of less than or equal to 1 point.
- Number and rate of patients with endoscopic improvement, by segment, and number and rate of patients with endoscopic remission, by segment, at Week 8 and at Week 16 (if available) per intervention/treatment group. Endoscopic improvement is defined as a Mayo endoscopic sub score of ≤1 (excluding friability) and endoscopic remission defined as sub score of 0.
- Number and rate of patients with mucosal healing. Mucosal healing is defined as both endoscopic remission and histological remission (Geboes score < 2.0).
- Reduction relative to baseline in stool and rectal bleeding frequency at every study visit by ABX464 dose group and versus placebo.
- Reduction relative to baseline in partial Modified Mayo Score at every study visit and Modified Mayo Score at Week 16 (if available) by ABX464 dose group and versus placebo.
- Reduction relative to baseline in fecal calprotectin and CRP levels at Week 8 and Week 16 by intervention/treatment group.
- Change relative to baseline in miRNA-124 expression in rectal/sigmoidal biopsies at Week 8 and Week 16 (if available) and in total blood at every timepoints by intervention/treatment group.
- The scores and changes from baseline in IBDQ at Week 8 and Week 16 per intervention treatment group.
- Reduction relative to baseline of infiltrate/histopathology (rectal/sigmoidal biopsies) using the Robarts Histopathology Index (RHI), the Geboes and Nancy Histology Scoring Scales at Week 8 and Week 16 (if available) per intervention/treatment group.
- Change relative to baseline in IL-6, TNF α , IL-1b, IL-10 plasma concentrations at every timepoints by intervention/treatment group.
- Serum concentration of ABX464 and ABX464-N-Glu according to dose group.
- Number and rate of all adverse events, causally-related adverse events, all SAE and causally-related SAEs classified by severity per intervention/treatment group.
- The incidence of treatment-emergent serious adverse event per intervention/treatment group.
- The incidence of adverse events leading to investigational medicinal product discontinuation per intervention/treatment group.
- The number of clinically-significant laboratory abnormalities per intervention/treatment group.

3. INVESTIGATIONAL PLAN

3.1. Study design

[figure not shown]
3.1.1. Design and methodology

This phase IIb study will evaluate the efficacy and the safety of 3 dose-levels of ABX464, administered daily in improving Modified Mayo Score (MMS) in patients with moderate to severe Ulcerative Colitis at Week 8.

Eligible patients will be randomized into 4 parallel intervention/treatment groups:

Intervention/treatment Active Arm	
Group #1: 25mg qd	1 capsule of 25mg ABX464 + 1 capsule of Placebo
Group #2: 50mg qd	1 capsule of 50mg ABX464 + 1 capsule of Placebo
Group #3: 100mg qd	2 capsules of 50mg ABX464
Group #4: Placebo	2 capsules of Placebo

The study design is presented below:

At Week 16, regardless of their clinical/symptomatic response and the actual treatment/dose received, patients willing to continue the study treatment and eligible for enrollment will roll over in an Open Label Extension study (ABX464-104). In this extension study, all patients will be dosed with ABX464 50mg QD. ABX464-104 is a separate clinical protocol subject to health authorities and ethics committee approvals.

In the present induction study (ABX464-103), randomization will be stratified according to the following factors:

- 1) US versus non-US patients
- 2) patients without previous exposure to biological or JAK inhibitors versus patients with previous exposure to biological drugs or JAK inhibitors.

The proportion of patients with previous exposure to biologics or JAK inhibitors will be limited to 60%, including a maximal proportion of patients with previous treatment with vedolizumab of 20%. The maximal proportion of patients with previous exposure with JAK inhibitors will be limited to 10%.

Patients will be treated for 16 Weeks in this induction study. All endoscopies (videos) will be centrally reviewed. E-Diaries will be used to collect frequency of stools, rectal bleedings, number of capsules taken and the intake time.

From Day 1 onwards, randomized patients will be seen at the investigational site on a regular basis (cf. flow-chart).

Flexible sigmoidoscopy with rectal and sigmoidal (if the sigmoidal is inflamed) biopsies will be performed at screening, at Day 57 +/- 4 days (week 8) and at Day 113 +/- 4 days (week 16). The Day 113 measurement will only be taken if patient does not experience endoscopic improvement at Day 57 (i.e.:

endoscopy sub-score of 2 or 3).

From Week 8 onwards, in the event of clinical progression of the disease defined as at least a 2-point increase from the screening in partial Modified Mayo Score (pMMS) with a Modified Mayo Score ≥ 4 confirmed by an endoscopy sub score of 2 points or higher, the patient will exit definitively the study.

Approximately 244 patients will be randomized in this study (i.e. 61 patients per study treatment arm).

3.1.2. Dose limiting toxicity (DLT)

A dose limiting toxicity (DLT) is defined as a grade 3 or higher adverse event as defined by the Common Terminology Criteria for Adverse Events (CTC-AE V5.0) considered by a safety review board as probably or definitely related to study treatment.

If more than 2 DLTs occur in the first five treated patients for at least 14 days, then the enrolment of additional patients in the concerned treatment group will be stopped, otherwise the enrolment of planned patients will be confirmed.

In addition, in case of a life threatening (grade 4) adverse reaction enrolment in the concerned treatment group and treatment of ongoing patients will be immediately discontinued.

In both cases, enrolment will only be resumed upon the decision of the sponsor if the Data Safety Monitoring Board can conclude that the causality of the event was unrelated or unlikely related to study treatment.

3.1.3. Data Safety Monitoring Board

An independent Data Safety Monitoring Board (DSMB), with expertise and experience in the pathology, and without direct involvement in the conduct of the trial, will be set up specifically to guarantee effective protection of patients, to ensure the ethical conduct of the trial, to evaluate the benefit/risk ratio of the trial, and to ensure the independent review of the scientific results during the trial and at the end of the trial. Besides, the DSMB may recommend the early termination of the trial at any time if an unacceptable toxicity occurs. The DSMB will meet every 2 months.

The DSMB will oversee the adequate balance of baseline characteristics (gender, disease duration, concomitant treatment with corticosteroids, fecal calprotectin level, tobacco use) among the treatment groups.

In addition, DSMB will be review all potential causally-related Serious Adverse Events within 7 days of the initial report.

The DSMB has only a consultative role. It will inform the Sponsor who will decide whether the DSMB recommendation will be followed. A DSMB charter must be available upon submission of the trial (initial protocol) to the respective competent authorities.

3.2. Duration of study participation

Eligible patients will be enrolled in the present study at the screening visit within 4 Weeks (28 ± 3 days) prior to the first dosing, hence the maximum screening period is 31 days. However, patients can be randomized anytime within the screening window if all examinations are performed as per their schedule and results are available. Patients will be treated for 16 Weeks. At Week 16, regardless of their clinical/symptomatic response and the actual treatment/dose received, patients willing to continue the study treatment and eligible for enrollment will roll over in an Open Label Extension study (ABX464-104). In this extension study, all patients will be dosed with ABX464 50mg QD.

In any other cases, patients will exit the study (EoS visit to be performed within a Week after last dosing) and will be treated according to the standard of care.

Thus, the total duration of the study participation is 21 Weeks.

4. STUDY POPULATION

4.1. Number of Patients/Centers

Up to 244 patients will be randomized in this study. These patients will be enrolled in approximately 110 to 150 sites located in Europe, Canada and in the USA.

4.2. Eligibility Criteria

4.2.1. Inclusion Criteria

A patient will be eligible for inclusion in this study only if ALL of the following criteria apply:

- Men or women age 18 - 75 years;
- Diagnosis of moderate to severe active UC (including ulcerative proctitis if proximal extension of disease occurs beyond 10 cm) confirmed by endoscopy and histology at least 12 Weeks prior to screening visit. Moderate to severe active UC defined by Modified Mayo Score (MMS) of 5 to 9 inclusive (on a scale of 0-9). Moderate to severe active UC should be confirmed at screening visit with a centrally read endoscopy sub-score of at least 2 (on a scale of 0-3);
- Patients having either a documented inadequate response, no response, a loss of response, or an intolerance (defined as the occurrence of at least one Adverse Reaction leading to treatment discontinuation) to either immunosuppressant treatment (i.e., azathioprine, 6-mercaptopurine, methotrexate), tumor necrosis factor [TNF] inhibitors, vedolizumab, JAK inhibitors and/or corticosteroid treatment. Inadequate response, no response, loss of response is defined as:
 - Active disease or relapse in spite of thiopurines or methotrexate given at an appropriate dose for at least 3 months (i.e. azathioprine 2–2.5 mg/kg/day or mercaptopurine 1–1.5 mg/kg/day in the absence of leukopenia), and/or
 - Active disease despite corticosteroids treatment (prednisolone up to 0.75 mg/kg/day) over a period of 4 Weeks, and/or
 - Active disease or relapse in spite of adequate treatment (as defined in the SmPC) with tumor necrosis factor [TNF] inhibitors or vedolizumab, and/or
 - Active disease or relapse in spite of adequate treatment with JAK inhibitors over a period of at least 6 Weeks.
- Patients receiving oral corticosteroids must have been on a stable dose of prednisone or prednisone equivalent (≤ 20 mg/day) or on beclomethasone dipropionate (≤ 5 mg/day) or on budesonide MMX (≤ 9 mg/day) for at least 2 Weeks prior to the screening visit;
- Topical corticosteroids and topical 5-aminosalicylic acid preparations must have been withdrawn at least 2 Weeks prior to the screening visit;
- Patients who are on oral 5-aminosalicylic acid must have been on a stable dose for at least 4 Weeks prior to the screening visit;
- Patients who are receiving immunosuppressants in the form of azathioprine, 6-mercaptopurine, or methotrexate needed to be on a stable dose for at least 4 Weeks prior to screening visit. Patients taking methotrexate also are advised to take folic acid 1 mg/day (or equivalent) supplementation if there is no contraindication;
- Patients on probiotics (e.g., Culturelle® [Lactobacillus GG, i-Health, Inc.], *Saccharomyces boulardii*) must be on stable doses for at least 2 Weeks prior to the screening visit;
- Patients on antidiarrheals (e.g., loperamide, diphenoxylate with atropine) must be on stable doses for at least 2 Weeks prior to the screening visit;
- Patients who have received tumor necrosis factor [TNF] inhibitors, vedolizumab or other biologics must have discontinued therapy at least 8 Weeks prior to the screening visit due to lack or insufficient efficacy or intolerance;
- Patients previously treated with cyclosporine, tacrolimus or JAK inhibitors must have discontinued therapy at least 4 Weeks prior to the screening visit due to lack or insufficient efficacy or intolerance;
- Patients previously treated with tube feeding, defined formula diets, or parenteral alimentation/nutrition must have discontinued treatment 3 Weeks before the screening visit and

must be able to take, orally, appropriate amount of food (calories) and liquids to maintain body weight;

- Patients with surveillance colonoscopy defined as per ECCO guidelines;
- Patients with the following hematological and biochemical laboratory parameters obtained at screening:
 - Hemoglobin > 9.0 g dL⁻¹;
 - Absolute neutrophil count \geq 750 mm⁻³;
 - Platelets \geq 100,000 mm⁻³;
 - Total serum creatinine \leq 1.3 x ULN (upper limit of normal);
 - Creatinine clearance $>$ 90 mL min⁻¹ by the Cockcroft-Gault equation within 60 days prior to baseline;
 - Total serum bilirubin $<$ 1.5 x ULN;
 - Alkaline phosphatase, AST (SGOT) and ALT (SGPT) $<$ 2 x ULN;
- Patients are able and willing to comply with study visits and procedures as per protocol;
- Patients should understand, sign and date the written voluntary informed consent form at the screening visit prior to any protocol-specific procedures are performed;
- Patients should be affiliated to a social security regimen (for French sites only);
- Females and males receiving the study treatment (potentially in combination with immunosuppressant) and their partners must agree to use a highly effective contraceptive method during the study and for 6 months after end of study or early termination. Contraception should be in place at least 2 Weeks prior to study participation. Women must be surgically sterile or if of childbearing potential must use a highly effective contraceptive method. Women of childbearing potential (WOCBP) will enter the study after confirmed menstrual period and a negative pregnancy test. Highly effective methods of contraception include true abstinence, intrauterine device (IUD) or hormonal contraception aiming at inhibition of ovulation, intrauterine hormone releasing system, bilateral tubal ligation, vasectomized partner. True abstinence is defined when this is in line with the preferred and usual lifestyle of the patient. In each case of delayed menstrual period (over one month between menstruations) confirmation of absence of pregnancy is required. This recommendation also applies to WOCBP with an infrequent or irregular menstrual cycle. Female and male patients must not be planning pregnancy during the trial and for 6 months post completion of their participation in the trial. In addition, male participants should use condoms and not donate sperm as long as contraception is required.

4.2.2. Exclusion Criteria

The following criteria should be checked at the time of screening. If ANY exclusion criterion applies, the patient will not be included in the study:

- Patients with Crohn's Disease (CD) or presence or history of fistula, indeterminate colitis (IC), infectious/ischemic colitis or microscopic colitis (lymphocytic and collagenous colitis);
- History of toxic megacolon, abdominal abscess, symptomatic colonic stricture or stoma; history or imminent colectomy, colonic malignancy;
- History or current evidence of colonic dysplasia or adenomatous colonic polyps. Patient with severe gastrointestinal complications; e.g., short bowel syndromes, recent or planned bowel surgery, ileostomy and/or colostomy, recent bowel perforation;
- History of more than one episode of herpes zoster or a history (single episode) of disseminated zoster;
- Patients with active infections at screening such as infected abdominal abscess, Clostridium difficile (stool antigen and toxin required), CMV (positive IgM), TB and recent infectious hospitalization;
- Patients previously treated with ABX464;
- Acute, chronic or history of clinically relevant pulmonary, cardiovascular, hepatic, pancreatic or renal functional abnormality, encephalopathy, neuropathy or unstable CNS pathology such as seizure disorder, angina or cardiac arrhythmias, active malignancy or any other clinically significant

medical problems as determined by physical examination and/or laboratory screening tests and/or medical history;

- Acute, chronic or history of immunodeficiency or autoimmune disease;
- History of malignancy excluding patients considered cured (5 years disease free survivors);
- Serious illness requiring systemic treatment and/or hospitalization within 3 Weeks prior to baseline;
- Pregnant or breast-feeding women;
- Illicit drug or alcohol abuse or dependence;
- Patients who received live vaccine 30 days or fewer before first dose of study treatment and/or who's planning to receive such a vaccine during the study duration;
- Use of any investigational or non-registered product within 3 months or within 5 half-lives preceding baseline, whichever is longer and during the study;
- Any condition, which in the opinion of the investigator, could compromise the patient's safety or adherence to the study protocol.

5. STUDY ASSESSMENTS AND PROCEDURES

5.1. Study Flow Chart

Table displays hereafter a detailed study flow chart (with all assessments).

Table 1: Study Flowchart

	Study Treatment Period								EOS (within a week after last dose)
	D-28	D1	D8	D29	D57	D85	D113		
Time Window	± 3 days		± 2 days	± 2 days	± 4 days	± 4 days	± 4 days		± 2 days
Obtained Inform Consent	X								
Check of IN/EX Criteria	X	X							
Physical Examination	X	X	X	X	X	X	X		X
Body Weight (kg)	X	X	X	X	X	X	X		X
Height Measurement (cm)	X								
Medical History and Concomitant Medications	X								
Clostridium difficile (stool antigen and toxin), CMV, TB	X								
Vital signs	X	X	X	X	X	X	X		X
ECG (12 lead)	X	X			X		X		X
Randomization		X							
Blood Pregnancy test (WOCBP)	X	X		X	X	X	X		FU
Hematology + Biochemistry	X	X	X	X	X	X	X		X + FU
Coagulation and Troponin		X	X	X	X	X	X		
Serum collection for patients with loss of response to biologics (neutralizing antibody)			X						
Modified Mayo Score (pMMSS/MMSS)	X [†]	X	X	X	X	X	X		X
e-Diary data collection	X	X	X	X	X	X	X		
Fecal calprotectin		X			X		X		X
Sigmoidoscopy	X				X			X	(Conditional)
IBDDQ		X			X			X	
ABX464/placebo treatment dispensation		X		X	X	X			
Blood samples drug pK	X*	X [#]	X [#]			X [#]	X*		
Blood sample Cytokines	X	X	X	X			X		
Samples for miRNA (Biopsy RNA Later)	X				X			X	
Samples for miRNA (Blood PAXgene tube)		X	X	X	X			X	
Adverse Events recording	X	X	X	X	X	X	X		X
Dermatologist Consultation in case of skin effect									

* Applicable to all randomized / D1: 0.5, 1.5, 3 h post-dose or 1, 2, 4 h post-dose; D113: pre-dose, 1, 2, 4 h post-dose or pre dose, 0.5, 1.5, 3 h post-dose. #: pre-dose only. FU = biological follow-up 3 Weeks after Day 120 (Hematology, Biochemistry and B-HCG) / No specific study visit required. [†]: pMMSS is calculated once within a week prior to screening endoscopy and Modified Mayo Score is calculated following endoscopy.

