5.2.4. Day 57 and Day 113 Visits

- IBD Questionnaire (as the first visit procedure);
- Physical examination and vital signs;
- Body weight;
- At Day 113, population Pharmacokinetics blood samples at either pre-dose, 1, 2, 4h and if possible 48 h (Day 115 only) or pre-dose, 0.5, 1.5, 3h and if possible 48 (Day 115 only);
- Hematology and Biochemistry including blood pregnancy test for all women of childbearing potential, coagulation parameters and troponin;
- Blood sample for miR-124 dosage (PAXgene® tube) and cytokines determination;
- 12-leads ECG;
- Fecal calprotectin;
- Sigmoidoscopy with rectal/sigmoidal biopsies (Day 113 endoscopy is conditional on the response at Day 57);
- Modified Mayo Score at Day 57 (and Day 113 if available; OR pMMS at Day 113 if Day113 endoscopy not performed);
- Check treatment compliance;
- Adverse Events reporting;
- Study treatment dispensation at Day 57 visit;
- Review the patient e-Diary;
- At Day 113, enrolment of patients willing to take part to the maintenance phase;
- Schedule next patient visits.

5.2.5. End of Study Visit (Within a week after last dose \pm 2 days)

This EoS visit applies to all premature discontinued patients and to patients not taking part to the maintenance study. Patients will perform an End of Study Visit (EoS) within a Week after last dosing (i.e D120 \pm 2 days if the patient completed the study and is not taking part in maintenance study). Patients will be treated according to the standard of care from the last day of study treatment.

Following examinations/procedures should be performed:

- Physical examination and vital signs;
- Body weight;
- Hematology and Biochemistry and a follow-up 3 Weeks later;
- Partial Modified Mayo Score;
- 12 leads ECG;
- Fecal calprotectin;
- Adverse Events reporting.

NB#1: In case of premature discontinuation occurring during the treatment phase (D1-D113), the above examinations should be performed as an End of Study Visit 7 days \pm 2 days after last dose.

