NB#2: A biological follow-up, including hematology, biochemistry panel and a pregnancy test (if applicable), should be performed according to the central lab manual 3 Weeks after EOS (i.e Day 120 if the patient completed the study and is not taking part in maintenance study). In case of premature discontinuation, this biological follow up should be performed 3 weeks after the last dose. No specific study visit is required. Potential Adverse Event or Clinically significant abnormal value should be reported according to the section 8.4 of the study protocol.

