8.1. Definitions

8.1.1. Definition of an AE

Any untoward medical occurrence in a patient or clinical investigation patient administered a pharmaceutical product and which does not necessarily have to have a causal relationship with this treatment.

An AE can therefore be any unfavorable and unintended sign (including an abnormal laboratory finding), symptom, or disease (new or exacerbated) temporally associated with the use of a medicinal product, whether or not considered related to the medicinal product.

Note: The official definition also extends to AEs occurring in the placebo arm. Because of regulatory requirements, events occurring during pre-and post-treatment periods will also be designated as AEs. Therefore, reporting of such events, AEs and SAEs, will commence when the patient is enrolled into the study (date of signature of the informed consent) up until 4 Weeks after the end of the treatment visits. The period after discontinuing study drug may be extended if there is a strong suspicion that the drug has not yet been eliminated.

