8.5. Time Period, and Frequency of Detecting AEs and SAEs

All AEs and SAEs occurring from the time a patient consents to participate in the study until 4 Weeks after he or she has completed or discontinued the investigational medicinal product must be recorded in the Patient's eCRF.

Moreover, any occurrence of pregnancy within 3 months post stopping dosing must be reported.

Importantly, SAEs will have to be reported, either by email or by Fax, to IntuVigilance Limited within 24 hours of awareness of an SAE.

IntuVigilance Limited

[name]
Hotline phone: [REDACTED]

Email Address: [REDACTED]

Fax number: [REDACTED]

Legislative guidance requires the investigator to also ensure that any **related** SAEs are reported after the patient finished the study if the investigator becomes aware of them.

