8.6. Recording AEs and SAEs

Severity of AEs will be assessed according to CTC-AE Classification Version 5.0.

Patients will be asked to report all AEs as part of the procedures performed at each study visit. The site personnel will document all AEs in the patient's medical record. All AEs subsequently must be recorded in the appropriate eCRF sections.

The following points must be recorded for each event:

- A description of the event in medical terms, not as reported by the patient;
- Date of onset (start date);
- Date of resolution (stop date);
- The time of onset with respect to administering the investigational medicinal product;
- The severity of the sign/symptom or clinically significant abnormal laboratory value according to CTC-AE Classification (Version 5.0);
- The causal relationship between the investigational medicinal product and the occurrence of each AE. This will be assessed by each investigator using clinical judgment. Alternative causes, such as natural history of the underlying diseases, concomitant medications, other risk factors and the temporal relationship of the event to the investigational medicinal product will have to be considered. The causality of all AEs should be assessed by the investigator with the following question: Is there a reasonable possibility that the AE may have been caused by the investigational medicinal product? And answered "NO" (if not related) and "YES" (if related);
- Action taken regarding the investigational medicinal product:
 - No action;
 - Temporary discontinuation;
 - Permanent discontinuation;

- Recovered without sequelae / resolved without sequelae;
- Recovered with sequelae / resolved with sequelae;
- Recovering/Resolving;
- On-going;
- Fatal (for SAEs only).

- Patient's outcome.

If in any one patient, the same AE occurs on several occasions, the AE in question must be documented and assessed a new each time.

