9.3. Safety Analyses

Adverse events will be coded using the standard dictionary (MedDRA) down to the lower level term (LLT).

An overall summary table will be presented (Any adverse event, any treatment emergent adverse event (TEAE), any serious adverse event (SAE), death, any grade 3 or higher adverse events from baseline to the end of Study. This analysis will be conducted on SAF population.

Two periods will be defined for TEAE:

- Any adverse event which occurs or worsens from first dosing to Day 113;
- Any adverse event which occurs after Day 113.

Adverse events will be described by primary system organ class and preferred term. Numbers and percentage of patients, and number of occurrences of adverse event will be presented for:

- TEAE;
- Serious TEAE;
- TEAE leading to drug discontinuation;
- TEAE of grade 3 or 4;
- TEAE for which relationship with the study drug is recorded as possible or probable;
- TEAE leading to death.

The assessment of safety will be based on the frequency of adverse events (with and without regard to causality) graded according to the CTC-AE Classification and also, the review of individual values for clinical laboratory data, vital signs and ECG focusing on the detection of abnormal values and PCSAs as determined upon investigator considerations.

Adverse events will be tabulated (counts and percentages) by group. All adverse events will be listed and the data will be tabulated by body system/organ class. Adverse event tabulations will include all treatment emergent adverse events, which will be further classified by severity, and relationship to treatment and dose level.

Clinical laboratory parameters, vital signs, ECG will be summarized by using descriptive statistics (n, mean, SD, SEM, median, minimum and maximum). Number of patients with at least one abnormal values will be tabulated (counts and percentages) for each parameter in summary shift tables, by group and dose.

9.3.1.Clinical laboratory evaluation

Descriptive statistics for laboratory parameters will be computed at each scheduled assessment. If relevant for some parameter, change from baseline will also be tabulated.

In addition, shift tables from baseline will be presented.

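### For patients not rolling over, adverse events must be recorded for 4 weeks after the last dose, but no one is scheduled to ask about them after about day 7

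*Protocol*

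**What the plan says.** **Recording window.** Protocol 8.5 has AEs and SAEs recorded from consent "until 4 Weeks after he or she has completed or discontinued the investigational medicinal product must be recorded in the Patient's eCRF". Protocol 8.1.1 gives the same length with a different starting point: "up until 4 Weeks after the end of the treatment visits".

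**Use in the analysis.** Protocol 9.3 defines two TEAE periods, the second being "Any adverse event which occurs after Day 113". SAP 17.1 treats an AE that starts after the last dose as treatment-emergent, giving the 4-week recording period as the reason. It flags events after Day 113 in the AE listing.

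**How AEs are elicited.** Protocol 8.6: "Patients will be asked to report all AEs as part of the procedures performed at each study visit".

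**Last visit.** Protocol 5.2.5: "Patients will perform an End of Study Visit (EoS) within a Week after last dosing". That is Day 120 ± 2 days for completers who do not roll over, and 7 ± 2 days after the last dose for early discontinuers. AE reporting is on the list of procedures. Protocol 7.3 exempts patients moving to ABX464-104 from this visit.

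**After the last visit.** The footnote to Table 1 in Protocol 5.1 describes the remaining contact: "FU = biological follow-up 3 Weeks after Day 120 (Hematology, Biochemistry and B-HCG) / No specific study visit required". NB#2 in Protocol 5.2.5 repeats that "No specific study visit is required" and adds that a potential AE or a clinically significant abnormal value should be reported under section 8.4.

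**The concern.** The recording obligation and the contact schedule do not match. A site that follows the schedule exactly asks about AEs for the last time about a week after the last dose. For the remaining three weeks of the mandatory window it hears of a symptom only if the patient volunteers it.

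The events at stake enter the TEAE summaries, because the SAP counts them as treatment-emergent. One of the protocol's own events of interest shows the difficulty. Protocol 5.3.2 asks for a questionnaire when a headache has lasted more than a week and is refractory to standard painkillers. A headache that starts after the last dose cannot yet have lasted more than a week at a nominal day-7 EoS visit, and no later enquiry is planned.

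The patients concerned are completers who do not enter the extension and all early discontinuers. The second group includes anyone who stopped because of an adverse event, and the safety profile by dose group is a stated objective (Protocol 2.2).

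**Working it through.** **The plan's own figure.** Protocol 3.2 states 21 weeks of participation. Screening 4 + treatment 16 + time to EoS 1 = 21 weeks, which reproduces it. Stated participation therefore ends at EoS. With the follow-up sample it would be 21 + 3 = 24 weeks.

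**Inputs**
- Recording window: 4 weeks = 28 days after the last dose (Protocol 8.5).
- Last dose: Day 113 (Protocol 6.1 and 7.1) or Day 112 (SAP 14).
- EoS: Day 120, window Day 118 to Day 122 (Protocol 5.1 and 5.2.5).
- Follow-up sample: 3 weeks after Day 120 (Protocol 5.1).

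**Share of the window after the last scheduled enquiry** = (28 − days from last dose to EoS) / 28

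| Last dose | EoS Day 118 | EoS Day 120 | EoS Day 122 |
|---|---|---|---|
| Day 113 | (28 − 5)/28 = 82% | (28 − 7)/28 = 75% | (28 − 9)/28 = 68% |
| Day 112 | (28 − 6)/28 = 79% | (28 − 8)/28 = 71% | (28 − 10)/28 = 64% |

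For early discontinuers, with EoS at 7 ± 2 days, the share is again 75%, range 68% to 82%.

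**Where the follow-up sample falls**
- Completers: Day 120 + 21 = Day 141. This is 141 − 113 = 28 days after a Day 113 last dose, or 29 days after a Day 112 last dose.
- Early discontinuers: NB#2 gives 3 weeks after the last dose, which is day 21. That leaves 28 − 21 = 7 days with no planned contact of any kind. The same note also gives 3 weeks after EoS, and the EoS procedure list in 5.2.5 says 3 weeks later. Counted from a day-7 EoS, that would be 7 + 21 = day 28. The two timings differ by a week.

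**What the follow-up contact looks for.** Hematology, biochemistry and hCG are tested, so laboratory abnormalities and pregnancy are actively sought. Section 8.4, to which NB#2 refers, deals with abnormal laboratory findings, other abnormal assessments such as vital signs, and pregnancy. Neither section tells anyone to ask about symptoms. In Table 1 the FU mark is on the laboratory and pregnancy rows and not on the AE row. The table is misaligned in the text available, so this is only supporting evidence; the footnote and NB#2 carry the point.

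**The case against.** The best defence is that the duty to record is already complete. Protocol 8.5 makes 4-week recording mandatory, section 8 makes the investigator responsible for detecting events, NB#2 links AE reporting to the follow-up sample, and 8.1.1 allows the period to be extended if the drug may not have been eliminated. Serious events would often come to light anyway. All of this stands as an obligation to report what becomes known. None of it schedules a question, and 8.6 places the question at visits.

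Several stronger readings are tempting, but the documents do not support them.

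- **That a separate table of TEAEs after Day 113 will be wrong.** Protocol 9.3 only defines the period, and SAP 17.1 plans a flag in a listing. Any loss would show in that listing and in the general TEAE summaries.
- **That events will be under-counted.** Spontaneous reporting could in principle capture everything. Likely under-ascertainment is as far as the text goes.
- **That about 76 patients are affected.** This carries over the phase IIa study, where 22 of 32 randomized patients entered the extension (Protocol 1.3): 10/32 = 31%, and 0.3125 × 244 = 76. The exact 95% interval for 10/32 is about 16% to 50%, or 39 to 122 patients. That study had an 8-week induction, and the reasons for not continuing are not fully given. The roll-over rate here is not stated.
- **That a third of the drug is still present when the questions stop.** Protocol 1.2.4 gives a half-life of 90 to 110 h for the metabolite in healthy subjects, and 2 to 3 h for the parent. Assuming first-order decay, 0.5^(168/90) = 27% to 0.5^(168/110) = 35% of the metabolite remains at day 7. It falls to 8% to 12% at day 14, 2% to 4% at day 21 and about 1% at day 28. Some metabolite exposure continues into the unasked period, but most of that period is at low exposure.
- **That the loss differs between arms.** It could, if the number not rolling over differs by dose. No figure in the documents shows that it does.

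**Conclusion.** The concern holds for patients who do not enter ABX464-104, and for non-laboratory events. Nominally 21 of the 28 days in the mandatory recording window (75%; 64% to 82% across the EoS window and the Day 112/Day 113 difference) have no scheduled enquiry. Late symptomatic treatment-emergent events are therefore likely to be under-ascertained. For early discontinuers, on the day-21 reading of NB#2, the last 7 days have no planned contact at all.

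The conclusion assumes that sites do what the schedule says and no more, and that the window runs from the last dose as in Protocol 8.5. Patients who roll over are outside it: they have no EoS visit in this study and continue on ABX464 under a separate protocol. The number of patients affected is unknown, a between-arm difference is possible but not shown, and the primary endpoint is not touched. This is an inexpensive improvement to safety ascertainment that should be made; it does not put the trial's main conclusion at risk.

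**What to change.** Add an AE/SAE enquiry as an FU entry on the AE row of Table 1, and state it in NB#2 of Protocol 5.2.5. It should apply to every patient not entering ABX464-104, early discontinuers included. It should be made at the end of the recording window, 28 days after the last dose, by telephone, or at the blood draw where that draw falls on day 28. Asking at the draw is not enough for early discontinuers if their sample is taken at 3 weeks, because days 22 to 28 would stay uncovered. Give the enquiry its own eCRF field, so that no event reported can be told apart from no question asked.

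Separately, reconcile the follow-up timing in Protocol 5.2.5 (3 weeks after EoS against 3 weeks after the last dose for early discontinuers), and align the starting point of the AE window in 8.1.1 with that in 8.5.

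The cost is one short call or question per patient not rolling over, one eCRF field, and slightly higher late AE counts. For patients whose sample is not on day 28, the call is a new contact.
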